4.1.3.1 MFM Database

This natural history database (described in a publication by Vuillerot et al. 2013) consists of SMA Type 1, 2 and 3 patients between 0 and 65 years of age with MFM data collected during real life clinical practice in 29 pediatric physical medicine departments in France, Belgium, Switzerland and Argentina since 2002. These centers use the MFM in the everyday management of patients with a wide variety of neuromuscular diseases, and their physiotherapists have been given specific training in administering the MFM with high intra-rater reliability.

This database also includes data from the Upper Limb Evaluation in Non-Ambulant Patients (ULENAP) study (ClinicalTrials.gov identifier: NCT00993161). The ULENAP study was a validation study sponsored by the Institute of Myology that aimed to develop a clinical test suitable for assessing upper limb function and strength in non-ambulant patients with neuromuscular diseases such as SMA and Duchenne muscular dystrophy (Seferain et al. 2015). During the study patients were assessed using several muscle strength measures and functional scales, including the MFM. The study includes SMA Type 2 and Type 3 patients between 8 and 30 years of age from 5 centers in France and Belgium. Patients were followed for a period of 12 months between 2010 and 2013.

4.1.3.2 NatHis-SMA

NatHis-SMA is a prospective natural history study sponsored by Roche and the Institute of Myology (Roche no. BP29540, ClinicalTrials.gov identifier: NCT02391831) that aims to characterize the disease course in SMA Type 2 and Type 3 patients using standardized evaluations, including the MFM. The study includes patients between 2 and 30 years of age from 9 centers in France, Belgium and Germany. Patients will remain in the study for a period of 12 to 24 months between 2015 and 2018.

4.1.4 Matched Patient Population

In order to account for differences between patients in the ITT population (treated) and those in the historical comparison population (untreated), several matching methods for

balancing baseline covariates will be considered depending on sample size, data availability and data quality.

If there is sufficient data, each individual in the ITT population will be matched to an individual in the historical comparison population (one-to-one matching) with respect to age, gender, SMA type and baseline MFM D1+D2 score. Gender and SMA type will be matched exactly, followed by optimal Mahalanobis distance matching within these groups for the age and baseline MFM D1+D2 score. In order to determine the 'closeness' between individuals to use in matching, we define the Mahalanobis distance, D_{ij} , between the i^{th} treated unit and j^{th} potential untreated unit:

$$D_{ij} = (x_i - x_j)^T \Sigma^{-1} (x_i - x_j)$$

where x_i and x_j are the observed values of the matching variables (age and baseline MFM D1+D2 score) for treated unit i and untreated unit j , respectively, and Σ is the variance covariance matrix of X in the untreated group. Optimal matching will be used to minimize the total distance $T = \sum D_{ij}$.

Patients in the ITT population who erroneously perform the MFM-20 assessment at the baseline visit will not be included in the matched patient population. MFM-20 assessments performed at any post-baseline visit will be set to missing.

If one-to-one matching does not produce enough matches (if > 10% of the ITT population is not matched), optimal full matching will be performed, where one untreated unit may be matched to more than one treated unit, but each treated unit will only be matched to one untreated unit. The maximum number of times each untreated unit is matched with a treated unit will be equal to the smallest integer value greater than or equal to the maximum ratio of treated to untreated units in each combination of gender and SMA type (Type 2 male, Type 2 female, Type 3 male and Type 3 female). The number of times each untreated unit is matched will be monitored to ensure that the treatment effect estimate is not based on only a small number of untreated units.

4.1.5 NatHis-SMA Comparison Population

The NatHis-SMA comparison population will include all patients enrolled in the NatHis-SMA study aged between the minimum age in the ITT population minus 2 years up to the maximum age in the ITT population plus 5 years, with Type 2 or non-ambulatory Type 3 SMA. This population will be used to evaluate the incidence of SMA related medical complications in olesoxime-treated patients compared to the natural history of the disease.

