## **3. STUDY DESIGN**

### **3.1 DESCRIPTION OF STUDY**

#### **3.1.1 Study Design**

This is an open-label, single-arm study to further evaluate long-term tolerability, safety, and efficacy outcomes in patients with SMA who previously participated in one of the following two clinical studies:

- Open-label Phase Ib, *multicenter, single- and multiple-dose study to assess safety and pharmacokinetics of olesoxime in pediatric and adult patients (6–25 years of age) with SMA (TRO19622CLEQ1115-1), and/or*
- Phase II/III, *adaptive, parallel-group, double-blind, randomized, placebo-controlled, multicenter, multinational study to assess safety and efficacy of olesoxime in pediatric and adult patients (3–25 years of age) with Type 2 and non-ambulatory Type 3 SMA (TRO19622CLEQ1275-1)*

The study will consist of Historical Data Collection, screening, treatment, and safety follow-up periods. The study will occur in approximately 23 sites in 7 countries in Europe. All patients who participated in the studies mentioned above will be invited to participate in this study. The maximum number of patients in this study will be 171.

A schedule of assessments is provided in [Appendix 1](#).

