4. STATISTICAL METHODS

4.1 ANALYSIS POPULATIONS

4.1.1 Intent-to-Treat Population

The intent-to-treat (ITT) population will include all patients who received at least one dose of study medication and have at least one post-baseline assessment of MFM. The ITT population will be the primary population for efficacy analyses.

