4.1.3 Historical Comparison Population

The historical comparison population will consist of SMA patients selected from natural history databases containing MFM data. This population will be used to select matches for patients in the ITT population in order to compare data collected during the study with natural history data describing motor function.

The historical comparison population will be chosen to match the ITT population as closely as possible with respect to age and SMA type. This population will include patients with Type 2 or Type 3 SMA (non-ambulatory) who have a confirmed diagnosis of SMA and at least two MFM measurements. The age range in this population will be restricted to a similar age range to that observed in the ITT population, with a minimum age of 6 years old or the minimum age in the ITT population minus 2 years (whichever is greater), up to the maximum age in the ITT population plus 5 years. Only patients with at least two MFM-32 assessments performed when the patient is non-ambulant and ≥ 6 years old will be considered for inclusion in the historical comparison population.

One patient will be selected from the natural history databases to match the patient from study TRO19622CLEQ1115-1 with Type 1 SMA. Gender will be matched exactly and

age will be matched within a window of 2 years. If there is more than one untreated patient meeting these criteria, one patient will be selected for inclusion in the historical comparison population using the following hierarchy:

1. The patient with the closest age,
2. The patient with the closest MFM D1+D2 score at baseline,
3. The patient with the closest baseline MFM assessment date,
4. A patient will be selected randomly.

The following data sources will be used to select patients for the historical comparison population:

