4.4.2.4 SMA Related Medical Complications and Procedures

SMA related medical complications and procedures will be collected through the adverse event (AE) reporting of the study and through the reporting of on-study SMA related surgeries and procedures. Events will be identified by applying a prospectively defined basket of MedDRA lowest level terms to the AE dataset and to the on-study SMA related surgery and procedure dataset.

For each event recorded, the term entered by the investigator describing the event (the 'verbatim term') will be assigned to a standardized term (the 'lowest level term') based on the most up-to-date version of MedDRA. Data displays of SMA related medical complications and procedures will be performed using the system organ class and lowest level terms. For summaries of event incidences, patients who experience the same event on more than one occasion will be counted once in the calculation of the event frequency at the highest intensity reported. Each table will also present the number and percentage of patients who experience at least one SMA related medical

complication or procedure during the study (including safety follow-up period) and the total number of events reported.

On-study SMA related surgeries and procedures which have not been identified by the MedDRA basket will be summarized separately.

Similar analyses will be performed for SMA related medical complications occurring in the NatHis-SMA comparison population. The pre-specified MedDRA basket will be applied to the AE dataset for this population, and the data will be summarized as described for the ITT population. AEs which have not been identified by the MedDRA basket and have been classified as 'due to the disease' by the investigator will also be summarized.

The AE rate adjusted for patient years (all occurrences, by lowest level term) and corresponding exact 95% CIs for the event rate in the ITT and NatHis-SMA comparison populations will also be presented. The event rate per 100 patient-years is computed as follows:

$$\text{AE rate} = (\text{number of AEs observed} / \text{total patient-years at risk}) * 100$$

where for study BN29854

Total patient-years at risk = sum across all patients of the time intervals (in years) between start of study therapy up to 28 days after study withdrawal/completion

and for the NatHis-SMA study

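### The SMA complications comparison sets the whole ITT population, which can include a Type 1 patient, beside natural-history patients limited to Type 2 and non-ambulatory Type 3 SMA

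*SAP*

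**What the plan says.** **Treated side.** SAP 4.1.1 defines the ITT population to "include all patients who received at least one dose of study medication and have at least one post-baseline assessment of MFM". Neither this definition nor the protocol's eligibility criteria (4.1.2, 4.1.3) limits SMA type or ambulation. Patients enter from two earlier studies. TRO19622CLEQ1275-1 took only Type 2 and non-ambulatory Type 3. Protocol 3.1.1 describes TRO19622CLEQ1115-1 only as assessing safety and "pharmacokinetics of olesoxime in pediatric and adult patients (6–25 years of age) with SMA".

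**Complications comparator.** SAP 4.1.5 takes NatHis-SMA patients in an age band derived from the ITT, "with Type 2 or non-ambulatory Type 3 SMA. This population will be used to evaluate the incidence of SMA related medical complications". SAP 4.4.2.4 applies the same MedDRA basket to them and says "the data will be summarized as described for the ITT population". It then presents rates per 100 patient-years, counting all occurrences by lowest level term, with exact 95% confidence intervals for each population.

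**MFM comparator.** SAP 4.1.3 starts from a similar restriction: "This population will include patients with Type 2 or Type 3 SMA (non-ambulatory) who have a confirmed diagnosis of SMA". It then makes an exception: "One patient will be selected from the natural history databases to match the patient from study TRO19622CLEQ1115-1 with Type 1 SMA". SAP 4.1.4 matches SMA type exactly.

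**The concern.** A natural-history comparison is only as good as the likeness of the two groups, and the simplest part of that likeness is a common eligibility rule. Here the rule binds the comparator alone. SAP 4.1.3 shows that the authors knew of a Type 1 patient and dealt with that patient for MFM. The complications analysis, which has no other protection against imbalance, makes no such provision.

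The comparison serves a stated secondary objective (Protocol 2.2). Protocol 1.1 describes Type 1 patients as never able to sit, often needing a feeding tube and typically having a shortened life expectancy. The complications of such a patient are of the kind this analysis counts. Because every occurrence counts, one patient with repeated events can move a term.

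**Working it through.** The plan gives no figure to reproduce: there is no powered sample size and no hypothesis test (SAP 4.4). The check compares the definitions and then bounds the effect.

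**1. The two comparisons side by side**

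| | MFM (SAP 4.1.3, 4.1.4, 4.4.1.2) | Complications (SAP 4.1.5, 4.4.2.4) |
|---|---|---|
| Treated side | drawn from the ITT | ITT |
| Comparator types | Type 2, non-ambulatory Type 3, plus one chosen Type 1 | Type 2, non-ambulatory Type 3 |
| Can the source supply Type 1? | yes, the MFM database includes Type 1 | no, NatHis-SMA covers Types 2 and 3 (SAP 4.1.3.2) |
| Matching | gender and type exact; age and baseline D1+D2 by Mahalanobis distance | none, age band only |
| Adjustment | SMA type, age, gender and baseline score in the MMRM | none, crude rates |
| Non-ambulant status required | comparator only | comparator only (Type 3) |

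The Type 1 imbalance is therefore confined to the right-hand column.

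**2. How many patients could be affected**

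- 165 patients were randomized in TRO19622CLEQ1275-1 (Protocol 1.2.2). The pool is 171 in Protocol 3.1.1 and 170 in SAP 2.2.
- Patients from outside that study: 171 − 165 = 6 (3.5%) or 170 − 165 = 5 (2.9%), ignoring deaths and overlap between the studies. These are potential entrants, not known enrolments.
- One of them is the Type 1 patient, which leaves 4 or 5 whose type and ambulation are not stated.

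**3. Assumed ITT size.** The documents do not give it. Protocol 1.2.2 reports baseline samples from 119 former TRO19622CLEQ1275-1 patients. If all are in the ITT, adding the Type 1 patient gives 120, and adding six gives 125.

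**4. Effect of the Type 1 patient on the crude rate.** Let R be that patient's event rate as a multiple of the others' rate (assumed), with equal follow-up. The relative increase is (N − 1 + R)/N − 1 = (R − 1)/N.

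| R | N = 120 | N = 125 | N = 171 |
|---|---|---|---|
| 2 | 0.8% | 0.8% | 0.6% |
| 3 | 1.7% | 1.6% | 1.2% |
| 10 | 7.5% | 7.2% | 5.3% |

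For a single lowest level term with E events in the other patients and e in this one, the rate is multiplied by (1 + e/E)(N − 1)/N. When E is small, e/E can be large. For the percentage of patients with an event, the shift is at most 1/N, about 0.8 percentage points.

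**5. If some of the others were ambulatory.** Suppose 4 of 124 or 5 of 125 were, with 0 to 0.75 times the event rate (assumed). The same formula gives 4/124 × (0.75 − 1) = −0.8% to 4/124 × (0 − 1) = −3.2%, and for five patients −1.0% to −4.0%. The direction is opposite to step 4.

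**The case against.** The strongest reply is that this concerns one patient in a descriptive table with no treatment-effect estimate and no test, in the population the plan declares primary for efficacy. On the assumption used here, the Type 1 patient also raises the olesoxime rate, so the distortion works against the drug. All of that stands, and it limits the size of the point. It does not explain why the mismatch was dealt with in one comparison and left in the other.

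Three stronger readings are tempting, and the documents do not support them.

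- *Both comparators omit Type 1.* They do not. SAP 4.1.3 adds a Type 1 control for MFM, SAP 4.1.4 matches type exactly, and type is also in the model.
- *Ambulatory Type 3 patients are being matched to non-ambulant controls.* SAP 4.1.3 does require of controls that "Only patients with at least two MFM-32 assessments performed when the patient is non-ambulant", and the treated side has no such rule. But no document shows an ambulatory patient, and by entry criteria one could come essentially only from the few TRO19622CLEQ1115-1-only patients. The baseline D1+D2 score, which covers standing and transfer, is a matching variable and covariate, and balance is checked. This is a gap in the wording, not a demonstrated bias.
- *The protocol singles out Type 1 for respiratory complications.* Protocol 1.1 calls respiratory failure and frequent pulmonary infections common in Types 1 and 2, and Type 2 is in the comparator. The higher event rate for Type 1 is therefore an assumption here.

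**Conclusion.** The point holds for the complications comparison. Its treated side can include a Type 1 patient for whom NatHis-SMA can offer no counterpart, and nothing in the analysis compensates. The patient's presence in the ITT is implied by SAP 4.1.3 but still depends on dosing and a post-baseline MFM assessment.

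The effect is minor: roughly 1% to 7% on the crude olesoxime rate, given an assumed 120 to 125 patients, an assumed 2- to 10-fold rate and equal follow-up. A rare term could move more. Any ambulatory patients would pull the other way, but the two effects cannot be relied on to cancel term by term. The matter is worth correcting because it is avoidable, not because it threatens the study's conclusions.

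**What to change.** In SAP 4.1.5 and 4.4.2.4:

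- Define the treated side of the incidences and event rates set beside NatHis-SMA as ITT patients with Type 2 or non-ambulatory Type 3 SMA.
- Keep the full-ITT summary as the study's own descriptive table, and list the Type 1 patient's events separately.
- State how ambulation is established. It is not an item in Protocol 4.4.3, Appendix 1 or SAP 4.3.2. Former TRO19622CLEQ1275-1 patients could be classified from that study's entry criterion, leaving site confirmation for the few TRO19622CLEQ1115-1-only Type 3 patients.
- If any of those is ambulatory, exclude that patient from this comparison and from the MFM matching to non-ambulant controls.

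Keep the Type 1 control in the MFM comparison. It is a deliberate provision and already solves the problem there.

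The cost is SAP wording, a short derivation rule and a little precision. If patients contribute events equally, losing one of 120 widens a rate's relative confidence interval by about √(120/119) − 1 = 0.4%. Losing six of 125 would widen it by about √(125/119) − 1 = 2.5%.

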2. STUDY DESIGN

Study BN29854 is a phase II, multicenter, open-label, single arm study to evaluate the long-term safety, tolerability and effectiveness of olesoxime (Roche No. RO7090919) 10mg/kg q.d. in patients with SMA who previously participated in one of the following two studies:

- Open-label phase Ib, dose-ranged, single and multiple dose study to assess safety and pharmacokinetics of olesoxime in 6-25 year old SMA patients (Trophos No. TRO19622CLEQ1115-1, Roche No. WP29845), and
- Phase II multicenter, randomized, adaptive, double-blind, placebo controlled study to assess safety and efficacy of olesoxime in 3-25 year old Type 2 or non-ambulatory Type 3 SMA patients (Trophos No. TRO19622CLEQ1275-1, Roche No. WN29836).

The study will consist of historical data collection, screening, treatment and safety follow-up periods. Patient visits will occur at 13, 26, 39 and 52 weeks and every 26 weeks thereafter for medical examinations, as well as safety and efficacy assessments. In addition, patients and their treating physicians will be requested to provide data for the period between the patients' last visit in the previous Trophos study and the screening period of study BN29854. Enrollment in the open-label treatment phase of the study is independent from the historical data collection, and a separate Informed Consent Form is required for each part. Patients (or their legal representatives) who do not consent to the historical data collection are still eligible to participate in the treatment phase of the study, and vice versa. The analysis methods that will be used for the historical data will be reported in a separate statistical analysis plan (SAP).

The study will continue until olesoxime is commercially available in the patient's country, or as per local regulation, or per the Sponsor's decision to terminate the olesoxime program for SMA, but will not exceed four years after the last patient was enrolled in the study. In the UK the study will last for a fixed period of three years after the last patient was enrolled.

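### The crude any-complication percentages for BN29854 and the unmatched NatHis-SMA cohort are not comparable if follow-up differs, and no time-adjusted any-complication measure is planned

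*SAP*

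**What the plan says.** Protocol 2.2 makes complications and procedures, compared with natural history, a secondary objective. Protocol 3.3.2.1 names the measure: the proportion of patients who have them.

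The comparator is set in SAP 4.1.5: "This population will be used to evaluate the incidence of SMA related medical complications in olesoxime-treated patients" relative to the natural course of the disease. It takes all NatHis-SMA patients with Type 2 or non-ambulatory Type 3 SMA, "aged between the minimum age in the ITT population minus 2 years up to the maximum age in the ITT population plus 5 years". The matching in SAP 4.1.4 (age, gender, SMA type, baseline MFM D1+D2) serves the MFM comparison only.

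Follow-up differs by design:
- NatHis-SMA (SAP 4.1.3.2): "Patients will remain in the study for a period of 12 to 24 months between 2015 and 2018".
- BN29854 (SAP 2): it may stop earlier but "will not exceed four years after the last patient was enrolled in the study". For one country, "In the UK the study will last for a fixed period of three years after the last patient was enrolled".

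SAP 4.4.2.4 then specifies two kinds of summary for both cohorts:
- Incidence tables. A patient with a repeated event counts once, at the highest intensity. "Each table will also present the number and percentage of patients who experience at least one SMA related medical" complication or procedure during the study, safety follow-up included. No common cut-off time is given.
- "The AE rate adjusted for patient years (all occurrences, by lowest level term"), per 100 patient-years, with exact 95% confidence intervals.

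The BN29854 events come from the AE dataset and the on-study surgery and procedure dataset. The NatHis-SMA events come from the AE dataset alone.

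**The concern.** The chance of having had at least one event grows with time under observation. If one cohort is watched for 12 to 24 months and the other for three or four years, the longer-followed cohort shows the higher percentage even when the underlying rates are identical. The same applies to counting at highest intensity, because a longer window can only raise a patient's maximum.

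The distorted quantity is the one Protocol 3.3.2.1 names as the efficacy measure, so the main reading of a secondary objective could hide a benefit or suggest a harm that is not there. Apart from the age range and SMA type used for selection, nothing balances the cohorts. Protocol 1.2.2 itself reports that patients aged 6 to 15 are more likely to worsen substantially, so age mix could matter.

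**Working it through.** **Inputs from the documents.** NatHis-SMA follow-up is 1 to 2 years (SAP 4.1.3.2). BN29854 follow-up is capped at 4 years after the last enrolment, with 3 years for the UK (SAP 2). BN29854 time at risk has a 28-day tail, 28/365.25 = 0.077 years (SAP 4.4.2.4).

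**Assumption.** The documents give no complication rate and no expected percentage for this comparison, so there is no plan figure to reproduce. I assume a constant first-event rate h, equal in both cohorts (no drug effect), and vary it. One figure for scale, on serious adverse events rather than complications: in the earlier randomised trial 29 placebo patients (50.9%, hence 29/57) had one over 24 months (Protocol 1.2.2). This gives h = -ln(1 - 29/57)/2 = 0.355 per year.

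**Formula.** P(at least one event by T) = 1 - exp(-hT).

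**At h = 0.3, without the tail:**
- T = 1: 1 - exp(-0.30) = 25.9%
- T = 1.5: 1 - exp(-0.45) = 36.2%
- T = 2: 1 - exp(-0.60) = 45.1%
- T = 3: 1 - exp(-0.90) = 59.3%
- T = 4: 1 - exp(-1.20) = 69.9%

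So 1.5 against 3 years gives 36% against 59%.

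**Range of rates, with the 28-day tail added for BN29854:**

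| h per year | NatHis-SMA 1.5 y | NatHis-SMA 2 y | BN29854 2 y | BN29854 3 y | BN29854 4 y |
|---|---|---|---|---|---|
| 0.1 | 13.9% | 18.1% | 18.8% | 26.5% | 33.5% |
| 0.2 | 25.9% | 33.0% | 34.0% | 46.0% | 55.8% |
| 0.355 | 41.3% | 50.9% | 52.2% | 66.5% | 76.5% |
| 0.5 | 52.8% | 63.2% | 64.6% | 78.5% | 87.0% |
| 1.0 | 77.7% | 86.5% | 87.5% | 95.4% | 98.3% |
| 2.0 | 95.0% | 98.2% | 98.4% | 99.8% | 100.0% |

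For rates of 0.1 to 1.0, the gap with no drug effect is about 8 to 16 points at 2 against 3 years, and about 20 to 35 points at 1.5 against 4 years. At 2.0 per year it falls to 1.6 and 5.0 points. With 2 years in both cohorts it is at most about 1.4 points (64.6 - 63.2).

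**Direction.** The percentages are equal when the rate ratio is T(NatHis-SMA)/T(BN29854). That is 2/3.077 = 0.65 at 2 against 3 years, and 1.5/4.077 = 0.37 at 1.5 against 4 years. Olesoxime would have to cut the rate by that much merely to look the same.

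**Does the planned patient-year rate cure it?** A simulation with no drug effect used 200,000 patients per cohort, with follow-up uniform on 1 to 2 years against uniform on 3 to 4 years plus 28 days:

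| h per year | Crude %, NatHis-SMA vs BN29854 | Rate per 100 patient-years |
|---|---|---|
| 0.2 | 25.8 vs 50.9 | 20.0 vs 19.9 |
| 0.355 | 40.9 vs 71.8 | 35.4 vs 35.5 |
| 0.7 | 64.3 vs 91.7 | 69.9 vs 70.0 |

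At a constant rate the follow-up artefact disappears from the rate and stays in the percentage.

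**The case against.** The strongest reply is that SAP 4.4.2.4 already plans an event rate per 100 patient-years with exact intervals in both cohorts, and defines time at risk for each. This stands. A reader might infer that the whole comparison is spoiled by unequal follow-up. The documents do not support that: the planned rate handles follow-up length for each term, provided the rate is constant over time.

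It can also be said that an overall all-occurrence rate follows from planned output, since each table gives the total number of events and the patient-years do not depend on the term. That is true, but it is not planned, repeat events in a few patients can drive it, and it does not give the proportion of patients affected.

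A reader might further infer that the percentages must differ. Four years is a ceiling, the study may stop earlier, and realised follow-up is not stated. If both cohorts are followed for about 2 years, the problem is negligible.

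Nor can the artefact manufacture an apparent benefit, because it works against olesoxime.

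On case mix, the comparator is restricted by age range, SMA type and ambulation, and SAP 4.3 plans baseline descriptions that would show an imbalance. Describing an imbalance does not adjust for it, but its effect cannot be sized from the documents. The one Type 1 patient mentioned in SAP 4.1.3 is a small matter.

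**Conclusion.** The concern holds for the crude any-event and highest-intensity percentages, on the condition that BN29854 follow-up exceeds that of NatHis-SMA. At an assumed 0.3 first events per patient-year, 1.5 against 3 years gives 36% against 59% with no drug effect. Over assumed rates of 0.1 to 1.0, the gap is roughly 8 to 35 points across the two follow-up contrasts shown. It shrinks at very high rates and nearly vanishes when follow-up is equal.

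Three gaps remain beside the planned rates:
- There is no time-adjusted version of the any-complication measure that the protocol names.
- Neither the percentages nor the rates are adjusted for age or SMA type. The size and direction of any resulting bias are unknown.
- The two cohorts draw on different event sources. The additional surgery and procedure dataset can only add to the BN29854 count.

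The conclusion rests on assumed, constant and equal rates. Constancy is itself uncertain, because the later BN29854 person-time comes from the same patients at older ages. The analysis is descriptive with no formal testing, so this is a matter of interpretability rather than error control.

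**What to change.** Amend SAP 4.4.2.4 for the NatHis-SMA contrast only:

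1. Replace the crude any-event percentages with cumulative incidence at 12 and 24 months in both cohorts (Kaplan-Meier, or with death as a competing risk). Add an overall any-complication rate per patient-year, for example first events over time to first event or end of follow-up. The 12-month figure will be the firmer one, since NatHis-SMA patients leave between 12 and 24 months.
2. Standardise or weight both measures to the ITT distribution of age and SMA type, and of sex and baseline MFM where numbers allow. Work within the age range both cohorts share and leave out the one Type 1 patient. The bands in SAP 4.4.5 start at age 6, whereas SAP 4.1.5 has no six-year floor, so those bands alone could miss younger comparator patients.
3. Apply the MedDRA basket to the AE dataset only, in both cohorts. Procedure data stay in the BN29854 tables.

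Keep the full-follow-up crude and highest-intensity tables for BN29854, with a label that they are not comparable with NatHis-SMA.

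The cost is SAP wording, a few extra tables from data already held, and slightly wider intervals. Later BN29854 years drop out of the cumulative-incidence contrast but remain in the single-cohort tables.
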